## **1.0   Protocol Summary and/or Schema**

This study is designed to test the efficacy and the cumulative toxicity of intrathecal (administered through Ommaya reservoir)  $^{131}\text{I}$ -3F8 in children and adult patients with GD2-expressing central nervous system/leptomeningeal neoplasms. Survival is extremely poor in these patients, with median survival of only a few months. In a prior phase I trial, 2 of 13 patients had negative remain alive and in complete remission after 4 years. Patients in this protocol will receive intrathecal  $^{131}\text{I}$ -3F8 weekly for a total of four treatment cycles. About 130 patients will be accrued on this study. The primary endpoint is overall survival at six months.

## **2.1 Objectives and Scientific Aims**

- To determine whether, in patients with GD2-expressing central nervous system/leptomeningeal neoplasms, the activity of intrathecal  $^{131}\text{I}$ -3F8 is sufficiently promising to warrant further study. Promising activity is defined as a 6 month overall survival rate of 25% or more.
- To determine the response rate to  $^{131}\text{I}$ -3F8 in this population.
- To determine the cumulative toxicities of serial injections of intrathecal  $^{131}\text{I}$ -3F8.
- To describe the effects of HAMA (human-anti-mouse antibody) on cerebrospinal fluid (CSF) and serum pharmacokinetics following multiple injections of  $^{131}\text{I}$ -3F8

## **3.1 Background and Rationale**

### **3.2 Disease background**

With the central nervous system as a sanctuary site, it is increasingly recognized that improved treatment of systemic cancers is associated with a higher incidence of central nervous system relapse and neoplastic meningitis. By the time neuraxis metastases are clinically evident, limited palliative options exist; median survival time for most malignancies is 4-14 months. Stereotactic radiosurgery for small, single metastases (<4cm diameter), surgery for solitary metastases and radiotherapy are used for palliation. New techniques including preoperative functional imaging, image-guided neurosurgery, intraoperative ultrasound and cortical mapping have improved the success of aggressive surgical resection, and lowered the associated surgical morbidity and mortality. However, novel therapeutic agents that may prevent or delay the progression of disease are needed to improve overall outcome.

### **3.3 Rationale for targeted immunotherapy**

Tumor-selective radioimmunotherapy strategies may have potential in inhibiting leptomeningeal tumor growth. The systemic administration of tumor specific monoclonal antibodies has proven useful in the detection and targeted treatment of many human tumors. GD2 expression has been demonstrated in neuroblastoma, small cell lung cancer, retinoblastoma, melanoma, high grade astrocytoma, medulloblastoma, osteosarcoma, desmoplastic small round blue cell tumor, and other sarcomas. Expression in normal human tissue is limited to nervous tissue. 3F8 is a murine IgG3 antibody against GD2. The intravenous administration of 3F8 has proven anti-tumor effects and has been incorporated into treatment strategies improving the disease-free survival for patients with metastatic neuroblastoma since 1989. Acute side effects including pain and urticaria are manageable. No long-term side effects have been observed over a 15 year period. 3F8 is easily labeled with I, enabling sensitive and accurate imaging.

### 3.4.2 Pharmacokinetics

Peak CSF radioactivity was generally achieved within the first hour of injection. After an initial antibody redistribution phase within the CSF compartment, the CSF biological half-life was 3-12.9 hours by direct CSF samples, and was in close agreement with the CSF gamma camera estimates derived from region of interest data (7.2-13.1 hours). The average radiation dose to the blood was 0.48 Gy (0.14-1.3). Activity levels in the blood remained low (<0.01% injected dose/cc), peaking 12-48 hours. The activity in the CSF fell much more rapidly than the physical half-life of 8 days; the concentration of the activity (uCi/cc) dropped by two orders of magnitude within 2-3 days after administration. The dose contribution for the time interval 72 hours to infinity was less than 10 %.

We concluded from the phase I study that intraventricular administration of  $^{131}\text{I}$ -3F8 targeting disialoganglioside GD2 achieves a favorable CSF to blood ratio, is associated with significant but manageable acute toxicities, and may have clinical utility in the treatment of some patients with GD2-positive LM cancers.

There are few other therapeutic options to offer this patient population. This study fills an unmet need at this institution for both pediatric and adult patients and capitalizes on Memorial Sloan-Kettering's Cancer Center's unique contribution to the field of targeted immunotherapy.

## **4.1 Overview of Study/Design Intervention**

### **4.2 Design**

This is a phase II single-arm open-label study that will define responses to therapy with weekly intrathecal  $^{131}\text{I}$ -3F8 in patients with central nervous system/leptomeningeal GD2-expressing disease. Dosimetry at plaques of disease and surrounding normal tissues will be determined by a pre-treatment  $^{131}\text{I}$ -3F8 (2 mCi) scintigraphy. Pharmacokinetics of the dosimetry

dose of intrathecal  $^{131}\text{I}$ -3F8 will be determined by measurements of counts per minute (cpm) of serial CSF and serum samples.

Patients will then receive intrathecal  $^{131}\text{I}$ -3F8 treatment cycle (10 mCi/cycle) approximately weekly for a total of 4 cycles. A total dose of 40 mCi  $^{131}\text{I}$ -3F8 will be administered. Since the phase I study demonstrated a CSF dose of 15-60 cGy/mCi to the CSF, maximum total anticipated CSF dose of  $4 \times 10$  mCi of  $^{131}\text{I}$ -3F8 injections would be 600-2400 cGy; dose to the spinal cord and normal brain is negligible given the short range path length of  $^{131}\text{I}$ . At an estimated tumor to CSF dose ratio of 5:1, tumor dose could be as high as 3000-12000 cGy. Myelosuppression is not anticipated at this dose level. The chosen 40 mCi maximum  $^{131}\text{I}$  dose is considerably lower than the MTD reported using other intrathecal  $^{131}\text{I}$ -monoclonal antibodies for neoplastic meningitis on other phase I studies. To avoid the risk of radiation toxicity in patients who have had previous craniospinal radiation, the CSF radiation dose delivered by  $^{131}\text{I}$ -3F8 therapy injections will not exceed 2400 cGy based on the CSF dosimetry estimates from pre-treatment  $^{131}\text{I}$ -3F8 / scintigraphy scans. This may require the elimination and/or dose reduction of the 3rd or 4th injection for patients who have had previous craniospinal radiation. There will be no dose modifications for patients who have not had craniospinal radiation. Response to therapy will be assessed by neurologic examination, radiographic imaging and CSF cytology analysis. Other aims will be met by monitoring patients clinically and biochemically for toxicity and by serum assessment of HAMA.

It is quite possible that  $^{131}\text{I}$ -3F8 may lead to disease stabilization without complete or partial responses in this population with advanced disease. We therefore propose overall survival at six months as the primary endpoint of this study. Leptomeningeal disease is rapidly fatal. Though some prior studies have reported survival at six months of around 15% these included patients receiving chemotherapy. Patients receiving  $^{131}\text{I}$ -3F8 at MSKCC have completed all chemotherapy and are not anticipated to have further oncologic treatment after progressing on this protocol. If  $^{131}\text{I}$ -3F8 has zero effect, we would therefore expect no more than 5% of patients to survive for six months. We will therefore use 5% overall survival at six months as the null hypothesis with 25% overall survival at six months as the alternative hypothesis.

Roadmap for the imaging dose of  $^{131}\text{I}$ -3F8

Day -5: Start SSKI and Liothyronine orally  
Day -1: Start Dexamethasone (start ~24 hrs pre-injection and tapered over ~1-2 days) orally  
Day 0: Injection of  $^{131}\text{I}$ -3F8 (2 mCi) intrathecally or by Ommaya

Roadmap for each weekly treatment cycle of  $^{131}\text{I}$ -3F8

Day -5: Start SSKI and Liothyronine orally  
Day -1: Start Dexamethasone (start ~24 hrs pre-injection and tapered over ~1-2 days) orally  
Day 0: Injection of  $^{131}\text{I}$ -3F8 (10mCi) intrathecally or by Ommaya

\* Dose adjustments for age <3 years based on CSF volume:

< 1 year: 50% dose reduction/injection

1-3 years: 33% dose reduction/injection

>3 years: Full dose 10 mCi  $^{131}\text{I}$ -3F8 per injection

\* Dose adjustments for patients with previous craniospinal radiation: The total maximum target CSF dose will be 2400 Gy. This may require a decrease or elimination of the 4th injection to prevent the risk of radiation toxicity for these patients. No dose adjustment will be made for patients who have not received prior craniospinal radiation.

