##### **4.2.1 Clinical Evaluation**

Patients will have pre- and post-treatment clinical assessment including neurologic examination, hematology and serum chemistries, and CSF analysis. Patients without objective disease progression and without unexpected grade 4 toxicity (controllable fever, headache, nausea, vomiting not included) will be eligible for a total of 4 treatment cycles. No patient will receive more than 4 treatment cycles.

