### **6.2 Patient /Subject Exclusion Criteria**

6.2.1 Patients with obstructive or symptomatic communicating hydrocephalus.

6.2.2 Patients with an uncontrolled life-threatening infection.

6.2.3 Patients who are pregnant: Pregnant women are excluded for fear of danger to the fetus. Therefore negative pregnancy test is required for all women of child-bearing age, and appropriate contraception is required during the study period.

6.2.4 Patients who have received cranial or spinal irradiation less than 3 weeks prior to the start of this protocol.

6.2.5 Patients who have received systemic chemotherapy (corticosteroids not included) less than 3 weeks prior to the start of this protocol.

6.2.6 Severe major organ toxicity. Specifically, renal, cardiac, hepatic, pulmonary, and gastrointestinal system toxicity should all be less than or equal to grade 2. Patients with stable neurological deficits (because of their brain tumor) are not excluded. Patients with  $\leq 3$  hearing loss are not excluded.

6.2.7 Patients must have no rapidly progressing or deteriorating neurologic examination.

6.2.8 Patients who have already received  $>45$  Gy to the craniospinal radiation or  $>72$  Gy focal brain radiation.

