### **\* Dose adjustments for patients with prior craniospinal radiation:**

The total maximum target CSF dose by  $^{131}\text{I}$ -3F8 injections will be 2400 Gy for patients with prior craniospinal radiation based on  $^{131}\text{I}$ -3F8/ scintigraphy dosimetry estimates. This may require a decrease or elimination of the 3rd or 4th injection to prevent the risk of radiation toxicity for these patients.

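### The CSF dose cap for patients with prior craniospinal radiation is 2400 cGy in the design narrative but 2400 Gy in both dose-adjustment instructions

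*Combined protocol and SAP*

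**What the plan says.** One cap for one group of patients appears three times in the combined protocol and SAP.

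- **Section 4.2, Design, narrative.** For patients with previous craniospinal radiation, the CSF dose from "therapy injections will not exceed 2400 cGy based on the CSF dosimetry estimates from pre-treatment" scans. The text adds that the 3rd or 4th injection may have to be reduced or dropped.
- **Section 4.2, dose adjustments listed after the roadmaps.** "The total maximum target CSF dose will be 2400 Gy". Only the 4th injection is named as one that may have to change.
- **Section 9.3, dose adjustments for prior craniospinal radiation.** The maximum from the "injections will be 2400 Gy for patients with prior craniospinal radiation based on" the scintigraphy estimates. The 3rd or 4th injection is named.

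The figures behind the cap are in the section 4.2 narrative. The "phase I study demonstrated a CSF dose of 15-60 cGy/mCi to the CSF", four cycles of 10 mCi are planned, and the maximum total anticipated from these "injections would be 600-2400 cGy; dose to the spinal cord and normal brain is negligible". At an assumed 5:1 tumor-to-CSF ratio, "tumor dose could be as high as 3000-12000 cGy". Section 4.2.1 adds that "No patient will receive more than 4 treatment cycles".

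**The concern.** The two places headed as dose adjustments are where staff would naturally look when comparing a patient's dosimetry with the limit, and both carry a unit that makes the limit 100 times larger than the narrative's. No passage acknowledges or reconciles the difference.

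The stated purpose of the cap is to avoid radiation toxicity in patients whose neuraxis has already been irradiated. It is the only dose adjustment that the protocol provides for that group. A reader who takes the number from either instruction would never find a patient over the limit, so no injection would be reduced or withheld on this ground. The patients affected would be previously irradiated ones whose individual CSF dose per mCi is unusually high, which is the case that the pre-treatment dosimetry is there to detect.

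**Working it through.** **Inputs**

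| Quantity | Value | Source |
|---|---|---|
| CSF dose per unit activity (phase I) | 15-60 cGy/mCi | Section 4.2, narrative |
| Planned therapy activity | 4 × 10 mCi = 40 mCi | Section 4.2, narrative |
| Tumor-to-CSF dose ratio | 5:1 | Section 4.2, narrative |
| Cap, narrative | 2400 cGy = 24 Gy | Section 4.2, narrative |
| Cap, both instructions | 2400 Gy = 240,000 cGy | Section 4.2, note after the roadmaps; section 9.3 |
| Prior-radiation exclusion limits | 45 Gy craniospinal, 72 Gy focal brain | Section 6.2.8 |

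**Step 1: reproduce the plan's figures.** Total CSF dose = dose per mCi × activity.

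- Lower end: 15 × 40 = 600 cGy.
- Upper end: 60 × 40 = 2400 cGy.
- Tumor dose: 5 × 600 = 3000 cGy and 5 × 2400 = 12000 cGy (120 Gy).

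All four match section 4.2.

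**Step 2: when does each version of the cap bind on a full course?** Threshold = cap ÷ 40 mCi.

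- Intended: 2400 ÷ 40 = 60 cGy/mCi, exactly the top of the phase I range.
- Printed: 240,000 ÷ 40 = 6,000 cGy/mCi, which is 100 times that top value.

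Put the other way, at 60 cGy/mCi the intended cap is reached at 2400 ÷ 60 = 40 mCi, or four injections. The printed cap would be reached at 240,000 ÷ 60 = 4,000 mCi, or 400 injections. A full course at 60 cGy/mCi uses 2400 ÷ 240,000 = 1% of the printed cap.

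**Step 3: which unit is meant?**

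- The cap in cGy equals the upper anticipated CSF dose from Step 1.
- Both instructions that print Gy also expect that a late injection may have to be cut. With a cap of 2400 Gy and a maximum of 40 mCi that could not happen, so each contradicts itself.
- 2400 Gy is 2400 ÷ 120 = 20 times the highest tumor dose the protocol anticipates, 2400 ÷ 45 = 53 times the craniospinal exclusion limit and 2400 ÷ 72 = 33 times the focal brain limit. The intended 24 Gy is 24 ÷ 45 = 53% of the craniospinal limit. These ratios compare different kinds of dose, so they serve only as a check on the scale of the unit.

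**Step 4: the difference in injection wording.** Three full injections (30 mCi) stay within 2400 cGy up to 2400 ÷ 30 = 80 cGy/mCi. Up to that value, changing the 4th injection alone is enough. Above it, the 3rd must be cut too, as the narrative and section 9.3 allow. The note in section 4.2 does not forbid this; it simply does not mention it.

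**Sensitivity.** These thresholds count therapy injections only, as the narrative does. If the 2 mCi dosimetry dose were counted as well, the intended cap would bind above 2400 ÷ 42 = 57 cGy/mCi, and the total at 60 cGy/mCi would be 60 × 42 = 2520 cGy. The unit conclusion does not change.

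**The case against.** The best case on the other side accepts the misprint and disputes its weight.

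- **The right value is in the document.** The section 4.2 narrative states the cap in binding terms, and nothing ranks the two instructions above it. The remark about cutting a late injection also shows a careful reader that Gy cannot be meant. This stands: the intended limit is recoverable. It does not make the other two statements correct.
- **Other limits hold whatever the cap says.** Each injection is 10 mCi, the total is 40 mCi and there are at most four cycles. This stands, and it is why the 100-fold ratio cannot be read as a possible overdose.
- **The intended cap would rarely bind.** On a full course it acts only above 60 cGy/mCi, outside the quoted phase I range, and the narrative regards the dose to cord and normal brain as negligible. This stands in part. All three passages nevertheless foresee cutting a late injection, and the protocol requires individual dosimetry rather than relying on the phase I range, so the limit is not idle.
- **Medical physicists calculate the dosimetry and would probably notice.** This is plausible, but a protocol limit should not depend on someone recognizing that it is wrong.
- **There is no statistical consequence.** Correct: the endpoint, hypotheses, sample size, alpha and power are unaffected.

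**Conclusion.** The point holds. The cap for patients with prior craniospinal radiation is printed in the wrong unit in both dose-adjustment instructions, and the protocol's own dosimetry shows that 2400 cGy is meant. The printed limit is 100 times the intended one and would bind on a full course only above 6,000 cGy/mCi instead of 60, so as written in those two places it gives no protection.

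This is an error in a safety threshold that should be corrected, not evidence of harm. The documents do not show that any patient was dosed against the wrong unit, and they do not say how many previously irradiated patients exceed 60 cGy/mCi. The thresholds assume a full 40 mCi course at one constant dose per mCi for each patient. The finding about the unit does not depend on that assumption. The mismatch over which injections may be changed is minor and adds nothing to the weight.

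**What to change.** In the dose-adjustment note in section 4.2 and the corresponding instruction in section 9.3, replace 2400 Gy with **2400 cGy (24 Gy)**. Giving both units guards against the same slip recurring. As a minor conforming edit, have the section 4.2 note refer to the **3rd or 4th** injection, as the other two passages do.

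The cost is two unit corrections and one wording change in a single amendment, with no extra patients, procedures or analyses.

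An optional precaution, not needed for the correction, is a one-time comparison of the CSF doses already delivered to previously irradiated patients with 2400 cGy.

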#### **4.3 Intervention**

Patients will receive 10mCi intrathecal  $^{131}\text{I}$ -3F8 per week. Patients will be pre-medicated with dexamethasone to prevent possible meningeal inflammatory reaction, Liothyronine and SSKI to prevent thyroid accumulation, and acetaminophen and diphenhydramine in anticipation of possible allergic reaction and fever.

##### **4.2.1 Clinical Evaluation**

Patients will have pre- and post-treatment clinical assessment including neurologic examination, hematology and serum chemistries, and CSF analysis. Patients without objective disease progression and without unexpected grade 4 toxicity (controllable fever, headache, nausea, vomiting not included) will be eligible for a total of 4 treatment cycles. No patient will receive more than 4 treatment cycles.

##### **4.2.2 Response**

MRI studies will be obtained at baseline and after the last injection. Stable disease may be an indicator of response, since most patients with leptomeningeal cancers (especially those with visible disease) historically die within a short time (4 weeks).

##### **4.2.3 Dosimetry**

Pharmacokinetics and dosimetry of the dosimetry dose of intrathecal  $^{131}\text{I}$ -3F8 will be determined by measurements of counts per minute (cpm) of serial CSF and serum samples and serial scintigraphy images obtained at approximately 4, 24 and 48 hours after injection. Dosimetry estimates will be calculated by Medical Physics physicists in the Dept of Nuclear Medicine.

#### **5.0 Therapeutic/Diagnostic Agents**

5.1  $^{131}\text{I}$ -3F8: IND # - BB-IND-2299

5.2 Source and pharmacology: Monoclonal antibody 3F8 is a murine IgG3 antibody. It is raised in BALB/c mice and specifically recognizes the ganglioside GD2.

5.3 Formulation and stability: 3F8 is stored as 2 mg/ml in pH 4.2 citrate phosphate buffer. Vials are stored at -80 C. 3F8 is stable at -80°C, and at -20°C for at least 2 years. For intrathecal administration,  $^{131}\text{I}$ -3F8 is diluted into 5% human serum albumin and millipore (0.2 um) filtered before use. Total anticipated amount to be infused per injection is 2-10 mCi, and about 2 mg of total (cold + hot) 3F8. .

5.4 Route of administration: A volume of ~1.0-4.0 ml will be administered intraventricularly via Ommaya catheter at a rate of ~1.0ml over 3-4 minutes using sterile technique. .

5.5 Supplier: 3F8 is commercially prepared by GBI as an investigational agent under cGMP conditions as required by the US FDA, and purified by column chromatography. All lots have to pass sterility, safety, pyrogen, murine viruses, and DNA testing before human use.  $^{131}\text{I}$ -3F8 is prepared by the Radiochemistry and Molecular Imaging Probes Core Facility under the direction of [name]. It is approved for human use via IND BB-IND-2299. Radiolabeling is performed either on the day of patient infusion or one day prior. Administration to patients occurs within 24 hours of the end-of-synthesis time..

## **6.0 Criteria for Subject Eligibility**

### **6.1 Patient/subject Inclusion Criteria**

6.1.1 Patients must have a histologically confirmed diagnosis of a malignancy known to express GD2. Such tumors include medulloblastoma/primitive neuroectodermal tumor of the CNS, high grade astrocytomas, malignant glioma, neuroblastoma, retinoblastoma, ependymoma, rhabdoid tumors, sarcomas, melanoma or small cell lung carcinoma. For patients with other tumor types, GD2 expression must be confirmed by immunohistochemical staining and assessed by the Department of Pathology using prior frozen tissue, bone marrow or CSF cytology (send to Research Lab).

6.1.2 Patients must have CNS/ leptomeningeal disease including high risk medulloblastoma, or a CNS/leptomeningeal malignancy which is refractory to conventional therapies, or for which no conventional therapy exists, OR a recurrent brain tumors with a predilection for leptomeningeal dissemination (medulloblastoma, PNET, rhabdoid tumor).

6.1.3 Patients must have an absolute neutrophil count (ANC) > 1000/ $\mu\text{l}$  and a platelet count > 50,000/ $\mu\text{l}$ .

6.1.4 Patients may have active malignancy outside the central nervous system.

6.1.5 Patients who have a programmable shunt will not be excluded.

6.1.6 Both pediatric and adult patients of any age are eligible.

6.1.7 Patients or a legal guardian will sign an informed consent form approved by the IRB and obtained by the Principal or a Co- Investigator before patient entry. Minors will provide assent.

### **6.2 Patient /Subject Exclusion Criteria**

6.2.1 Patients with obstructive or symptomatic communicating hydrocephalus.

6.2.2 Patients with an uncontrolled life-threatening infection.

6.2.3 Patients who are pregnant: Pregnant women are excluded for fear of danger to the fetus. Therefore negative pregnancy test is required for all women of child-bearing age, and appropriate contraception is required during the study period.

6.2.4 Patients who have received cranial or spinal irradiation less than 3 weeks prior to the start of this protocol.

6.2.5 Patients who have received systemic chemotherapy (corticosteroids not included) less than 3 weeks prior to the start of this protocol.

6.2.6 Severe major organ toxicity. Specifically, renal, cardiac, hepatic, pulmonary, and gastrointestinal system toxicity should all be less than or equal to grade 2. Patients with stable neurological deficits (because of their brain tumor) are not excluded. Patients with  $\leq 3$  hearing loss are not excluded.

6.2.7 Patients must have no rapidly progressing or deteriorating neurologic examination.

6.2.8 Patients who have already received  $>45$  Gy to the craniospinal radiation or  $>72$  Gy focal brain radiation.

